6.1.1 Screening/Dispensing Visit

A Screening and Enrollment Log will be provided by the Sponsor to track all consented subjects that the Investigator interviews regarding the study and completed study visits for enrolled subjects. Once the Screening and Enrollment Log is complete and all data is reviewed and confirmed by the field CRA, the Investigator will sign and date the form verifying the documented data is correct. The Investigator will retain a copy (yellow copy) of the original document for their records and the field CRA will submit the original to ClinDatrix.

After obtaining written informed consent, prospective subjects will be screened to determine whether they meet the entry criteria for the study.

The Screening/Dispensing Visit will proceed as follows:

NOTE: All VA measurements MUST be made using a phoropter.

- a. Enter the following information on the next available line of the Screening and Enrollment Log:
 - Subject Number
 - Subject Initials
 - Subject Date of Birth (DOB)
 - Gender
 - Habitual Lens Group
 - Visit 1 (Screening/Dispensing) Date
- b. Collect demographic information and record in the subject's source document.
- c. Collect the following baseline lens/lens care history information and lens wear parameters from the subject and record in the subject's source document:
 - Average daily wearing time
 - Hours lenses worn on the day of this visit
 - Average hours of comfortable wear
 - Current lens brand, sphere power and base curve
 - Current lens care products

- d. Perform the following baseline assessments (without lenses; remove the lenses if the subject wore lenses to the visit) and record in the subject's source document:
 - Spherocylindrical refraction
 - High contrast distance best spectacle-corrected visual acuity (BSCVA)
 - Keratometry
- e. Perform a slit lamp examination (remove the lenses if the subject wore lenses to the visit). Record and sketch any scars and slit lamp findings greater than Grade 2 in the subject's source document.
- f. If the subject continues to be eligible, have the subject complete and initial the following form:
 - The Initial Symptoms/Complaints Form (Worn Lenses Symptoms/Complaints Form), including use of rewetting drops.

Site personnel will transcribe this information to the Visit electronic Case Report Form (eCRF), and will retain the original in the study files.

- g. Complete the Initial Lens Performance Assessment Form (Worn Lenses Performance Rating Scales).

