- h. Dispense three pairs (two for back up only) of the subject's habitual contact lenses. Explain to the subject that the used lenses will be removed at the follow-up visits and returned to the Sponsor.
- i. Instruct subject to insert study lenses.
- j. Instruct subject to complete Symptoms/Complaints Form (Abbreviated version: Study Lenses Symptoms/Complaints).
- k. Complete the Lens Performance Assessment Form (Study Lenses Performance Rating Scales).
- l. Record the following into the subject's source documentation:
 - Dispensed lens type (brand), sphere power, base curve
 - High contrast distance lens VA
 - Over-refraction and distance VA
 - Lens wettability
 - Lens centration
 - Lens movement
 - For each eye, compare the high contrast distance lens VA to the high contrast Distance Best Spectacle-Corrected VA obtained at this visit. If the VA has decreased by 5 letters (0.1 logMAR) or more, explain.

- m. Indicate on the Screening and Enrollment Log whether the subject is a "Screen Pass" or "Screen Fail." Only "Screen Pass" subjects should be randomized in the study. "Screen Fail" subjects are ineligible and cannot be randomized in the study. No eCRFs shall be completed for "Screen Fail" subjects.
 - *If the subject is a "Screen Pass":* Log into ORS to randomize the subject. Enter the subject number from ORS on the Screening and Enrollment Log.

- *If the subject is a “Screen Fail”*: the reason for screen failure must be documented on the Screening and Enrollment Log and in the subject record, and maintained with a copy of their ICF.
- n. If the subject is a “Screen Pass” the Unmasked Designee should then dispense Study Kit bottles 1, 2, 3, and 4 only (keeping bottle 5 as a reserve at the site) (refer to Section 4.4.2) to the subject and record in the subject’s individual Product Accountability Log.
- o. The Unmasked Designee will explain to the subject that:
 - Cartons and bottles are NOT to be opened in front of any other site personnel.
 - The subject should retain all study materials during the course of the study.
 - Prior to coming to the site for the 3-month, exit or early study termination/suspension visits, follow-up visit or exit visit the subject should: (i) place all used and unused study solution bottles into their original white cartons, (ii) place the cartons and all lens cases into the opaque white drawstring return bag, (iii) close the bag, and (iv) return it to the unmasked designee.

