8.3.1 Overall Comfort

When the sample size in each group is 226, a two group 0.025 one-sided t-test will have 96.82% power to reject the null hypothesis that the test is not non-inferior to the standard (the difference in means, $\mu_{TT} - \mu_{TS}$, is -5 or farther from zero in the same direction) in favor of the alternative hypothesis that the test is non-inferior, assuming that the expected difference in means is 0 and the common standard deviation is 13.9.

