8.6.1.2 Overall Comfort

At each follow-up visit, overall comfort will be assessed for each eye on a scale from 0 to 100, with 100 denoting the most favorable response. For each eye, mean overall comfort over all follow-up visits will be computed as the average of the non-missing values over all scheduled follow-up visits. Missing data will not be imputed for the primary analysis. Mean overall comfort over all follow-up visits will be summarized at the eye level by treatment using continuous summary statistics for the Per Protocol Set in a table. A one-sided lower 97.5% confidence limit around the difference in means between the test and control treatment groups, computed using an analysis of variance model including the fixed factor of treatment and the fixed blocking factor of site, will be displayed. If the lower confidence limit is greater than -5.0, then the null hypothesis that the test solution is not non-inferior will be rejected, and the test solution will be statistically successful in this outcome.

As a sensitivity analysis, the ITT Population will be analyzed for this endpoint. Summaries by treatment and a confidence interval around the difference in means will be provided as described above using the available data. Twenty-five imputations of missing overall comfort data will be produced using the Markov chain Monte Carlo (MCMC) method with a seed of 1674236965. The variables used to create the imputed datasets will be the randomized treatment assignments (categorical), the subject identification numbers (categorical), and the overall comfort scores observed at each scheduled visit. The differences and standard errors estimated by imputation will be combined to create an estimated difference and confidence limit.

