8.6.1.3 Dryness

At each follow-up visit, dryness will be assessed for each eye on a scale from 0 to 100, with 100 denoting the most favorable response. Dryness will be analyzed using the methods described above for overall comfort. The seed for multiple imputation will be 1975251391.

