Compare high contrast distance lens VA to high contrast VA at Screening/Dispensing Visit			X	X			X	

[figure not shown]
PROCEDURES / ASSESSMENTS	Screening/Dispensing	2-Week Follow-up Visit	1-Month Follow-up Visit	2-Month Follow-up Visit	3-Month Follow-up Visit	Exit Visit	Unscheduled Visit	Post Study Follow-Up Visit
	Day 0	Day 10-18	Day 26-34	Day 53-67	Day 83-97			
Study Materials								
Dispense Lenses (record lens brand, sphere power, base curve); If replacement lens, record reason for replacement	X		X	X			X	
Dispense Study kit bottles 1, 2, 3 and 4 (keep bottle 5 as a reserve at the site);	X							
Dispense Study Kit reserve (Bottle 5, if needed)		X	X	X			X	
Dispense other supplies as needed (see Protocol Section 4.4.3)	X	X	X	X			X	
Collect worn lenses from subject			X	X	X	X	X	
Collect used and unused bottles of study solutions					X	X		
Return study materials to sponsor					X	X		

[figure not shown]
^a At the screening visit, only complete the Exit Form if the subject was randomized.

[figure not shown]
^b Use provided rating scales (separate document).

[figure not shown]
Note: All VA measurements MUST be made using a phoropter.

[figure not shown]
Note: If this is an Exit Visit, also perform the procedures listed under the Exit Visit column.

[figure not shown]

[figure not shown]

[figure not shown]

[figure not shown]

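### The comfort and dryness models omit the worn-lens symptom rating taken before randomisation, so they give up precision and leave any realised baseline imbalance in the estimate

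*Combined protocol and SAP*

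**What the plan says.** **Model.** For overall comfort (8.6.1.2), the one-sided lower 97.5% limit for the treatment difference is "computed using an analysis of variance model including the fixed factor of treatment and the fixed blocking factor of site". The outcome for each eye is "computed as the average of the non-missing values over all scheduled follow-up visits", so the screening value is not part of it. The decision rule is: "If the lower confidence limit is greater than -5.0, then the null hypothesis that the test solution is not non-inferior will be rejected". For dryness, 8.6.1.3 states: "Dryness will be analyzed using the methods described above for overall comfort".

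**Ratings before randomisation.** In 6.1.1, step f has the subject complete "The Initial Symptoms/Complaints Form (Worn Lenses Symptoms/Complaints Form), including use of rewetting drops". Step j adds an abbreviated form once the new lenses are in, and randomisation follows at step m. In Appendix A, footnote b ("Use provided rating scales (separate document") is attached to the Initial form and to the follow-up form, but not to the abbreviated form.

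**Other uses of baseline data.** Section 8.6.2 summarises baseline characteristics descriptively by treatment. Randomisation is stratified by lens group within site (8.4), not by symptoms. The multiple imputation in 8.6.1.2 uses comfort scores from each scheduled visit and does not say whether screening counts as one. Section 8.6.1.1 leaves further detail to a separate analysis plan, due before unmasking, which is not among the documents reviewed.

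**The concern.** Comfort and dryness are subjective 0 to 100 self-ratings. A person who rates high or low at screening can be expected to do much the same later, so the screening score should predict the follow-up average. Because it is recorded before allocation, treatment cannot influence it, and it is a legitimate covariate.

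Leaving it out has two consequences for two of the four primary tests. The residual variance, and so the distance from the estimate to its confidence limit, is larger than it need be against a margin of 5 points. And if the arms happen to differ at baseline, part of that difference is carried into the reported treatment difference, with nothing in the primary analysis to remove it.

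**Working it through.** **Inputs from the plan (8.3 to 8.3.6).** 226 eyes per group (113 subjects), margin 5, true difference 0, SD 13.9 (comfort) and 14.0 (dryness), one-sided alpha 0.025, eyes assumed independent.

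**Inputs assumed, because the documents do not give them.** Baseline-to-follow-up correlation *r* within arm and site, 0.3 to 0.7; baseline SD equal to the outcome SD; between-eye correlation *c*, 0 to 1.

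**1. Reproduce the plan's power.** The plan states: "When the sample size in each group is 226, a two group 0.025 one-sided t-test will have 96.82% power to reject the null hypothesis". SE = 13.9 × √(2/226) = 1.308. The noncentrality is 5/1.308 = 3.82 on 450 degrees of freedom, which gives 96.82% and agrees with the plan. For dryness, SE = 14.0 × √(2/226) = 1.317 and power is 96.63%, against 96.62% stated. The stated power is therefore correct for the unadjusted analysis under the plan's assumptions.

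**2. Precision with the covariate.** Residual SD = SD × √(1 − r²).
- r = 0.4: √0.84 = 0.917, an interval about 8% shorter.
- r = 0.6: √0.64 = 0.80, an interval 20% shorter.

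Power under the plan's eye independence:

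| r | Residual SD, comfort | SE | Power, comfort | Power, dryness |
|---|---|---|---|---|
| 0 | 13.90 | 1.308 | 96.8% | 96.6% |
| 0.3 | 13.26 | 1.247 | 97.9% | 97.8% |
| 0.5 | 12.04 | 1.132 | 99.3% | 99.2% |
| 0.7 | 9.93 | 0.934 | 99.96% | 99.96% |

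**3. Size of a chance baseline difference.** SE of the arm difference at baseline = 13.9 × √((1 + c)/2) × √(2/113):
- c = 0: 1.31 points
- c = 0.8: 1.75 points
- c = 1: 1.85 points

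With equal SDs, the amount carried into the unadjusted contrast is r times the baseline difference. At r = 0.5, a one-SE imbalance carries 0.65 points (c = 0) to 0.92 points (c = 1). The 95% range is ±1.3 points (c = 0) to ±1.7 points (c = 0.8).

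**4. What a realised imbalance does to the error rate.** Take a true difference of −5 and a valid SE. Given a baseline difference *d* in favour of Test, the chance of wrongly concluding non-inferiority is 1 − Φ[(1.96 × SE − r × d)/(SE × √(1 − r²))]. At r = 0.5:
- d = +2: 8.4% (c = 0) or 5.4% (c = 0.8)
- d = −2: 0.1% (c = 0) or 0.2% (c = 0.8)

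Averaged over randomisations, the rate is 2.5%.

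**5. Why the eye-level standard error matters to the remedy.** If the two eyes of a subject correlate and are analysed as independent, the one-sided error is 1 − Φ(1.96/√(1 + c)), which is 7.2% at c = 0.8. A covariate does not cure that. With a valid subject-level SE at c = 0.8 and 113 subjects per arm, comfort power is 81.0% unadjusted. With adjustment it is 84.5%, 90.6% and 97.8% at r = 0.3, 0.5 and 0.7.

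**The case against.** The main objection is that an unadjusted, prespecified model is valid in a randomised trial. A valid standard error already contains chance variation in habitual comfort, and the plan's own power leaves little to gain. Lost precision makes non-inferiority harder to show, so the sponsor bears the cost. All of this stands, and it limits the point to efficiency and to the imbalance that actually occurs.

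A reader might infer more: that subjects arrive from varied care products with no run-in, so baseline adjustment is the only protection, and that chance differences push the result towards or away from the margin. The documents do not support that. Allocation is randomised within site and lens group, both arms switch under the same rules, and nothing shows that switching affects one arm more than the other. The shifts in step 3 are part of the sampling error that the interval is meant to cover. The raised conditional error in step 4 has a mirror image when the imbalance favours Control.

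Three practical objections also stand in part.
- **The item content is not shown.** The rating scales are a separate document. That the Initial form carries the same comfort and dryness items is a reasonable inference from footnote b, not a demonstrated fact. The abbreviated form lacks that footnote, so it is not an assured substitute.
- **Some baseline ratings may be missing or recalled.** Section 6.1.1 allows for subjects who arrive without lenses, and step f comes after lens removal and the examinations.
- **Part of the gain may already be taken.** Site is in the model and may absorb some of the same variance. The imputation may already include screening, and the separate analysis plan may add an adjusted analysis. None of these changes the primary model fixed in 8.6.1.2.

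**Conclusion.** The point holds as a matter of precision and of protection against a realised imbalance. It is not bias, nor an error in the stated power. Adjustment would shorten the interval by about 8% to 20% if r is 0.4 to 0.6. Under the plan's eye independence, comfort power would rise from 96.8% to about 98% to 99% at r of 0.3 to 0.5. If the eyes are analysed validly and correlate strongly, the gain is worth more: at c = 0.8 and r = 0.5, power rises from 81% to about 91%. Eye correlation is a separate matter, however, and the case for the covariate does not depend on it.

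These sizes rest on an assumed correlation, an assumed baseline SD and the inferred content of the Initial form. The statement that the contrast is unbiased refers to the randomised comparison. The primary set is per protocol, so it also assumes that exclusions do not differ between arms in a way related to the outcome.

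**What to change.** Before unmasking:

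1. Confirm that the Initial (worn-lens) form carries the 0 to 100 comfort and dryness items, and whether they are rated per eye.
2. In 8.6.1.2 and 8.6.1.3, add the pre-randomisation worn-lens score for the same item as a covariate, alongside treatment and site.
3. State how a missing baseline score is handled, so that subjects without a worn-lens rating are not dropped by default.
4. Fit the model on subject means or with a subject term, so that the gain is not taken on an interval that counts two eyes as independent.
5. State that the screening score is among the imputation variables for the ITT sensitivity analysis.

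The unadjusted result can be kept as a supportive analysis. The cost is a change to the protocol and analysis-plan text, plus the handling of the few subjects without a worn-lens rating. If step 1 is confirmed, no new data, visits or subjects are needed. If the form does not carry the items, the covariate is not available in this form and the model should stay as it is.

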8.6.1.3 Dryness

At each follow-up visit, dryness will be assessed for each eye on a scale from 0 to 100, with 100 denoting the most favorable response. Dryness will be analyzed using the methods described above for overall comfort. The seed for multiple imputation will be 1975251391.

8.6.1.4 Lens Deposits

At each follow-up visit, lens deposits degree will be assessed for each eye as none, light, medium, or heavy. Using only the non-missing observations from scheduled follow-up

visits without imputation, each eye will be classified with respect to the maximum observed grade of Deposits at All Follow-up Visits (None or Light, Medium or Heavy). Missing data will not be imputed for the primary analysis. Maximum Deposits over All Follow-up Visits (None or Light, Medium or Heavy) will be summarized at the eye level by treatment using categorical summary statistics for the Per Protocol Set in a table. A one-sided lower 97.5% confidence limit around the difference in None or Light Deposits proportions between the test and control treatment groups will be constructed using the Newcombe-Wilson score method.² If the lower confidence limit is greater than -10.0%, then the null hypothesis that the test solution is not non-inferior will be rejected, and the test solution will be statistically successful in this outcome.

As a sensitivity analysis, the ITT Population will be analyzed for this endpoint. Summaries by treatment and a confidence interval around the difference in means will be provided as described above using the available data. The effects of missing data will be explored by considering best case and worst-case imputation scenarios. If the statistical conclusion differs between the best and worst-case scenarios, then a tipping point analysis will be completed.

8.6.1.5 Graded Slit Lamp Findings > Grade 2

At each follow-up visit, graded slit lamp findings will be assessed for each eye using Grades 0 through 4. Using only the non-missing observations from all visits without imputation, each eye will be classified with respect to findings greater than grade 2 at any visit (Absent, Present). Missing data will not be imputed. Greater than grade 2 findings (Absent, Present) will be summarized at the eye level by treatment using categorical summary statistics for the Safety Set in a table. A one-sided upper 97.5% confidence limit around the difference in “Present” proportions between the test and control treatment groups will be constructed using the Newcombe-Wilson score method.² If the upper confidence limit is less than 5.0%, then the null hypothesis that the test solution is not non-inferior will be rejected, and the test solution will be statistically successful in this outcome.

8.6.2 Subject Demographics and Baseline Characteristics

Demographics and baseline characteristics will be summarized descriptively by treatment and overall for the ITT, PP, and Safety Populations. Demographics and baseline characteristics will also be listed.

8.6.3 Subject Discontinuation

The reasons for study discontinuation will be summarized by treatment and overall for the ITT Population. Details of discontinued eyes will be also listed by treatment.

8.6.4 Protocol Deviations

Important (major) protocol deviations will be summarized by category and treatment group for the ITT Population in a table.

Categories of important protocol deviations will include the following, which will be derived via data entered on the case report forms.

- Ineligibility
- Not dispensed study treatment
- Misrandomization

- Dispensing of the incorrect solution
- Dispensing and use of lenses from the incorrect lens group
- Use of medications that could potentially affect any of the primary effectiveness endpoints
- Failure to comply with the procedures used to assess the primary effectiveness endpoints, such as missing the scheduled visit or failing to complete the procedure in accordance with instructions

Additional important protocol deviation categories may be added prior to unmasking.

Important (major) protocol deviations will also be displayed in a listing.

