3.2.3 Subject Discontinuation

A subject MAY be discontinued (at the discretion of the Investigator, the Sponsor, and/or the IRB) prior to the final study visit for a variety of reasons, including, but not limited to:

- An adverse event (AE) occurring during the course of the study, which precludes continued treatment or follow-up
- Persistent grade 3 or 4 slit lamp findings (must be reported to the Sponsor within 24 hours)
- Persistent study related symptoms/complaints
- Unacceptable distance lens visual acuity (VA)
- Unacceptable lens centration
- Unacceptable lens movement
- Other reasons related to failure to follow study procedures

A subject MUST be discontinued prior to the final study visit for any of the following reasons:

- Voluntary withdrawal
- Death
- Investigator decision that it is not in the best medical interest of the subject to continue participation in the investigation
- Ineligible at baseline - does not meet the eligibility criteria in the protocol
- Inability to maintain recommended wearing schedule
- Lack of motivation
- Continued failure to follow subject instructions
- Misses any follow-up visit
- Lost to follow-up (refer to Section 3.2.4)
- Instillation of non-medically indicated solution not specified in the protocol
- Either eye is discontinued
- Becomes pregnant during the study

Prior to discontinuing a subject, every effort should be made to contact the subject, schedule a final study visit, obtain as much follow-up data as possible, and to retrieve all study materials. Adverse events will be followed as described in Section 7.0.

Subject discontinuations will be documented clearly on the source document and applicable eCRF. The Investigator should indicate the PRIMARY (one) reason that the subject was discontinued for each eye. Subjects that are discontinued from the study following randomization will not be replaced.

Exit Visit assessments should be completed for early discontinued subjects, if possible.

3.2.4 **Lost to Follow-up**

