6.4 Concomitant Medications/Therapy

Other ocular solutions, medications or drops are not allowed to be used by subjects during the study. Use of other contact lenses are not allowed.

Ocular medications, systemic or topical medications that, in the Investigator's opinion, could potentially affect ocular physiology or lens performance are also prohibited, unless medically necessary during the course of the study. If used during the course of the study, these medications must be recorded in the source document and the appropriate eCRF.

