7.2 Adverse Event Treatment and Culturing

With any AE, treat the subject as appropriate to prevent further complications and to potentially resolve the event consistent with the standard of care.

For purposes of this study, the Sponsor requests that cultures should be obtained in cases of corneal ulcer or suspected ocular infection, unless medically contraindicated. Cultures should be taken from the cul-de-sac, lower eyelid margin, and the corneal lesion (if applicable). The required culturing techniques are outlined in Appendix B.

When a culture is obtained, the contact lenses and contact lens cases which were being utilized by the subject at the time of the AE should be collected from the subject for culturing and processing by the local clinical laboratory designated by the site.

Microbial data generated from returned subject supplies (e.g. lenses, lens cases, and/or lens case solutions) are for information only. Because microbes may be introduced into subject supplies during use, recovery of microbes from returned subject supplies cannot be presumed to indicate etiology or direction of organism transmission.

The ocular cultures, along with the associated contact lenses and contact lens cases, will be sent to the local clinical laboratory designated by the site for analysis. The clinical laboratory will report the culture results to the Investigator who will record the results in the eCRF.

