8.5.2 Per Protocol (PP) Population

The PP population will be the primary population used for analysis of the primary effectiveness endpoints. The PP Population will consist of all ITT Population subjects without important (major) protocol deviations for subject level summaries and, for eye level summaries, both of their eyes. Important protocol deviation categories are defined in Section 8.6.4 below (page 41). Subjects will be included in PP Population summaries according to the treatment group to which they were randomly assigned. The PP population will be determined prior to study unmasking.

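### Medication given to treat an on-study ocular adverse event can, with no exception, remove a subject and both eyes from the per-protocol analyses on which non-inferiority is declared

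*Combined protocol and SAP*

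**What the plan says.** Section 6.4 opens with a general ban: "Other ocular solutions, medications or drops are not allowed to be used by subjects during the study". Its next paragraph says that ocular, systemic or topical medications which the investigator thinks "could potentially affect ocular physiology or lens performance are also prohibited, unless medically necessary during the course of the study", and requires any use to be recorded in the source document and eCRF. Section 7.2 directs sites: "With any AE, treat the subject as appropriate to prevent further complications".

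Section 3.2.3 makes exit for an adverse event discretionary. Among its compulsory exits, the one about unlisted solutions is limited to "Instillation of non-medically indicated solution not specified in the protocol". A subject who is treated for an ocular event and stays on study is therefore foreseen.

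Section 8.6.4 includes among the important (major) deviations "Use of medications that could potentially affect any of the primary effectiveness endpoints". No exception for medical necessity is attached. Section 8.5.2 states: "The PP Population will consist of all ITT Population subjects without important (major) protocol deviations". It applies this to both eyes and adds: "The PP population will be the primary population used for analysis of the primary effectiveness endpoints". Sections 8.6.1.2 to 8.6.1.4 attach the success rule for comfort, dryness and deposits to the PP confidence limit and call the ITT analyses sensitivity analyses.

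**The concern.** Most of the other categories in Section 8.6.4 concern eligibility, randomization, dispensing or procedures. This one can be set off by a reaction to the assigned solution, in a subject who attends every visit and is treated as Section 7.2 asks. If Test irritated more eyes than Control, more Test subjects would be excluded, and they would tend to have the low comfort and dryness scores. Their removal raises the Test mean and moves the comparison towards non-inferiority. Fixing PP before unmasking prevents selection by arm. It does not prevent bias from a rule whose trigger is related to arm.

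Section 8.6.7 chooses PP without imputation on the ground that imputation is not conservative for non-inferiority. An exclusion linked to poor tolerance works against that aim.

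**Working it through.** **The plan's own figure.** Section 8.3.1 has 226 eyes per group, SD 13.9, margin −5, true difference 0 and one-sided α of 0.025. The noncentral t calculation gives 96.82% power, as stated. The sample size is not in dispute.

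**Shift in mean comfort.** Let f be the excess fraction of Test subjects excluded for this reason, and D the amount by which their eye-level average lies below that of the remaining Test subjects. If the retained Test mean is m, the mean with everyone kept is (1 − f)m + f(m − D) = m − fD, so exclusion raises the Test mean by fD. The documents give neither f nor D; both are assumptions here.

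D refers to an average. Section 8.6.1.2 averages the non-missing scores over the scheduled follow-up visits, and Section 3.4 schedules four. A 30-point fall at one visit of four therefore gives D = 30/4 = 7.5, and only a 30-point fall at every visit gives D = 30.

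| Assumed pattern | Arithmetic | Shift (points) | Share of 5-point margin |
|---|---|---|---|
| f = 5%, one visit, one eye | 0.05 × 7.5 / 2 | 0.19 | 4% |
| f = 5%, one visit, both eyes | 0.05 × 7.5 | 0.375 | 7.5% |
| f = 2%, every visit, both eyes | 0.02 × 30 | 0.6 | 12% |
| f = 5%, every visit, both eyes | 0.05 × 30 | 1.5 | 30% |
| f = 10%, every visit, both eyes | 0.10 × 30 | 3.0 | 60% |

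**Chance of passing on comfort.** Suppose the retained Test subjects are equal to Control. PP then compares 226(1 − f) Test eyes with 226 Control eyes at a true difference of 0. With everyone kept, the difference is −fD, the Test variance is 13.9² + f(1 − f)D², and the chance of passing is approximately Φ((5 − fD)/SE − 1.96).

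- One visit, both eyes, f = 5%: SE = √[(13.9² + 0.05 × 0.95 × 7.5² + 13.9²)/226] = 1.312, and (5 − 0.375)/1.312 − 1.96 = 1.565. That is 94.1% with everyone kept, against 96.5% in PP.
- Every visit, both eyes, f = 2%, 5%, 10%: 90.8%, 71.9%, 28.5% with everyone kept, against 96.7%, 96.5%, 96.0% in PP.

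PP stays near 96% throughout because it no longer contains the affected subjects.

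**Deposits, as an upper bound.** Section 8.3.3 assumes 0.925 with none or light deposits in each arm. If every removed eye would have been medium or heavy, f = 5% gives a Test proportion of 0.925 × 0.95 = 0.879 with everyone kept. The chance of passing is then 46.7%, against 96.9% in PP. A treated reaction need not produce deposits, so this is an extreme.

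**Can scores recorded before medication show the reaction?** Sections 6.1.2 to 6.1.4 place the subject's symptom form ahead of adverse event collection and the slit lamp examination. When treatment starts at a scheduled visit, that visit's form can already reflect the reaction. When it starts between scheduled visits, the retained scores may all predate the reaction.

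**The case against.** A reader might infer that every use allowed by Section 6.4 becomes a major deviation. The text does not say so. Section 8.6.4 reaches only medication that could affect a primary effectiveness endpoint, whereas Section 6.4 asks about ocular physiology or lens performance. Treatment without medication does not trigger the category. What stands is that the threshold is low, and drops given for an eye reaction would probably meet it.

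A reader might also infer that these subjects disappear from the effectiveness evaluation. They do not. They stay in the ITT sensitivity analyses of all three endpoints. They also stay in the Safety Population, where findings above grade 2 count towards the slit lamp endpoint. Section 8.6.4 already plans a table of important deviations by category and arm. These safeguards limit the harm without removing it. Milder reactions do not count in the slit lamp endpoint, no rule says what follows if ITT and PP disagree, and the table would not separate adverse event treatment from prohibited use.

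It is also fair to say that ocular drops can alter comfort and dryness, so setting aside scores taken under medication is a defensible PP convention. That supports setting aside the later scores, not deleting the earlier ones.

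Finally, the scenario is narrow. Subjects who miss a visit or cannot keep the wearing schedule must exit under Section 3.2.3 and would not be restored by a change here.

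**Conclusion.** The gap is real: a stated rule can remove subjects from the deciding analysis because of an effect of the solution, in the direction that favours non-inferiority. It merits correction before unmasking.

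Its size cannot be determined from the documents. At an assumed 5% excess in Test, the shift in mean comfort is about 0.2 to 0.4 points for a reaction that lowers one of four visits by 30 points, and 1.5 points if every visit is lowered. Quoting 1.5 points alone would overstate the matter, because that requires an average more than two SDs (30/13.9 = 2.2) below the other subjects in both eyes. The pass probabilities further assume that the retained Test subjects match Control and, as the plan does, that eyes are independent. Nothing in the documents shows that Test causes more treated reactions.

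**What to change.** All of this is analysis definition, with no change to care, and can be settled before unmasking:

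1. Reconcile Sections 6.4 and 8.6.4, so that medication given to treat an ocular adverse event arising on study is not by itself an important deviation for PP. The two paragraphs of Section 6.4 also need to be reconciled with each other; which medication rule applies is for the sponsor to state.
2. Keep these subjects in PP with all scheduled scores recorded up to the medication start date, including the form completed at the visit where treatment began. Section 6.4 already requires the medication to be recorded.
3. Repeat the PP analysis with their later scheduled scores included, and show it beside the primary result.
4. In the planned deviation table, separate adverse event treatment from prohibited use, by arm.

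The cost is a sentence or two in Section 8.6.4, one extra table, a few more low scores in PP and a slightly larger variance. One limit remains: reactions treated between scheduled visits are captured only in the analysis under item 3, so it should not be left out.
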